Participants assigned to both groups will have: 1) reduced unmet needs, 2) reduced depressive symptoms, and 3) higher levels of satisfaction with care at 6 months than their baseline assessment values.

Caregivers assigned to CC+C will have greater reductions in caregiver burden at 6 months than those assigned to CC alone. Indicators of relationship strain (e.g., marital distress and/or mutuality) will show greater improvement in CC+C than CC at 6 months. 6 month gains in shared pleasant events, social engagement, and quality of life will also be greater in CC+C than in CC alone. 6-month desire to institutionalize will be lower in the CC+C group than those randomized to CC. Treatment engagement (e.g. action plan completion, attendance) is also predicted to be higher in the CC+C group than in CC.

For Aim 3, we anticipate that individuals who receive the CC+C intervention will have lower rates of placement in long-term care facilities at 6 and 12 months than those who receive CC alone. We also expect that behavioral problems will impact treatment outcomes such that those dyads with higher levels of behavioral disturbance at baseline will have greater change scores at 6 months. Spousal relationship to the veteran is also expected to moderate treatment outcome such that spousal caregivers are anticipated to have lower change scores compared to non-spousal caregivers across time; however, we expect this effect to be attenuated in the CC+C condition.

7. Background, including results of relevant research, gaps in the current knowledge.

Scope of the Problem

Over five million Americans are diagnosed with Alzheimer's disease or a related disorder (ADRD) and rates are expected to triple by 2050¹. It is the 6th leading cause of death in the United States and one in three older adults will have dementia when they die².

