r. The 6-item **Desire to Institutionalize (DTI)** Scale⁵¹, which assesses the caregivers planning, thoughts, and actions about long-term care (LTC) placement over the past 6 months will be used to assess intentions to institutionalize their loved one. Six yes/no items (e.g., taken steps toward placement) are summed for a score of 0-6. Long-term care placement and/or hospitalization of the veteran (institutionalization) will be assessed using a single item rated either by the caregiver or via electronic health record review if the dyad is no longer enrolled in the study (e.g., due to attrition).

s. The 21-item **Care Consultation Satisfaction Survey** will be used to measure the participants' satisfaction with the Care Consultant and the Care Consultation services provided.

Once baseline data are collected, dyads will be randomly assigned to a condition (see interventions delivered below).

Randomization

Blocked randomization stratified by race and gender will be used to assign participants to either the: (a) CC group, or the (b) CC+C group. This two-group experimental design was chosen over other approaches (e.g., no comparison group designs, three-group design, cross-over design, etc.) because it most closely approximates the next level of clinical research (e.g., an efficacy study), which allows for the most directly applicable conclusions.

Interventions Delivered

1. Care Consultation (CC): is an established telephone-based, empowerment intervention that uses coaching and emotional support to mobilize family caregivers and individuals with dementia through psychoeducation, resource referral, psychosocial support, and encouragement of informal and formal service use utilization. A computerized clinical tool utilizing a password-protected VA-hosted website (i.e., operated within the VA server system) called the Care Consultation Information System (CCIS) guides the care consultant through a standardized delivery of protocol components, replacing a paper-based clinicians manual. Rather than a strong focus on assessment, this intervention is designed to quickly identify areas of unmet need through brief trigger questions called the “initial assessment” – much like an interview guide – which then immediately shapes development of concrete action plans.

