The CCIS has been successfully used by the TADO team clinically at the TVAMC. Fidelity reviews, technical support, and problem-solving are available on an ongoing basis through a nominal annual renewal fee. Care consultation has demonstrated robust outcomes across community and VA settings (e.g., Partners in Dementia Care, PIs [name] & [name] both on the study team) and has been translated successfully beyond research protocols into clinic settings.

2. Care Consultation + Counseling (CC+C): is consistent with the original CC protocol and a collaborative recovery model in that the therapist partners with each dyad in a patient-centered way to prioritize unmet needs as identified during the CC initial assessment. Once this phase has been completed, typically within the first 2 sessions, the CC+C therapist will determine when to initiate counseling (Table 2, below). The counseling component of the recovery-informed CC+C intervention incorporates elements of existing manualized interventions that follow a cognitive behavioral therapy framework (i.e., active engagement, assigning in-session and out-of-session exercises, reframing or restructuring cognitions, interpreting, and educating). The therapist has the flexibility to individualize care such that immediate needs identified by the dyad at the beginning of the care consultation partnership will take priority. For many families this will mean that concrete action plans related to CC domains of care (e.g., arranging benefits, questions about medication) will be implemented before the counseling protocol is initiated. Based on preliminary clinical work in the TADO clinic, it is expected that the course for most cases will follow three phases:

1. Phase 1: Care Consultation (initial assessment and addressing immediate practical needs);
2. Phase 2: Counseling (to address distress and mental health needs beyond the scope of CC alone);
3. Phase 3: Care Consultation (to maintain progress, provide ongoing support, and continue to address lingering needs or those that surface for the first time after core distress elements have been addressed).

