Including the individual with dementia is encouraged in CC and CC+C, though many of the original resource materials available focus on the skill development for the caregiver. To continue movement toward a dyad-focused approach in CC+C, phone sessions with the veteran with dementia will be completed whenever possible either before or after the caregiver phone session. Though shared sessions may be possible for some dyads, and more readily available in the future with videoconferencing technology, sequential interactions will be the focus of CC+C.

Table 2. CC+C Session Content

Telephone Session Content (approximately 6-8 Sessions)
1. Introduction to Stress Management (required): Impact of dementia on relationships, impact of stress on caregiving, and introduction to stress management/skills.
2. Mindfulness (required): What is mindfulness, types of mindfulness, and mindfulness in everyday activities.
3. Increasing Pleasant Activities (required): Introduce how discomfort and mood are related to activity level, explore current activity, and discuss ways to modify activities for greater comfort and enjoyment.
4. Grief & Loss (required): ambiguous loss, identifying grief-related emotions, shifting roles & needs fulfillment; disconnect between expectations and current course.

5. Preserving Identity (required): Values/goals; maintaining individual identity of the caregiver and person with dementia, documenting memories, and creating shared meaningful/pleasant activities.
6. Physical Affection & Sexual Intimacy (elective): Touch as nonverbal communication and social connection, building intimacy through shared rituals/routines.
7. Managing Chronic Pain and Distress (elective): Pain education and distress behaviors as indicators of pain.
8. Resentment, Hostility, & Conflict Resolution (elective): Lean about arguments you cannot win; hurtful lapses in memory, accusations & paranoia, and impact of previous patterns of relating on current relationship; commitment to relationship, etc.
9. Alcohol, Substances, and Medications Misuse (elective): Safety planning and management of alcohol/substance of abuse, the impact of memory problems on management of medications and an introduction to resources for sustained support.

Treatment Implementation, Fidelity, and Process Variables:

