Treatment delivery: The MSW-level interventionist will be trained to criterion and will be certified before administering the intervention. Accuracy of treatment delivery will be monitored. The interventionist will also complete a fidelity checklist to ensure that all treatment components are delivered during each session. As one measure of potential bias, the treatment fidelity checklist will include a self-reported item assessing the interventionists' desire/pressure to alter the randomly assigned condition for each dyad (i.e., agreement with the following statement will be assessed: "I believe the other arm of the study would have been a better fit for this dyad than the one they were randomly assigned"). Sessions will be audiotaped and 30% of sessions will be randomly selected and reviewed to ensure treatment fidelity to the CC and CC+C protocols. Treatment receipt: will be assessed by documenting the length of all intervention sessions (i.e., direct time spent with the dyads) and indirect time (e.g., documentation, case management, etc.). Participant knowledge of interventions components, which is sometimes included in measures of treatment receipt, is not appropriate for this study.¹¹⁰ Treatment enactment: will be monitored by: 1) the number of completed Action Plans and homework assignments in each group CC & CC+C, and 2) attendance/adherence to scheduled appointments. Other treatment implementation notes that do not directly impact human subjects protections include interventionists notes about "Process Considerations and Interventionist Pressures" including the interventionists' opinions about the two interventions (CC and CC+C).

18. Differentiation of "usual (standard) care" from research activities.

All procedures listed are voluntary in nature and unrelated to current clinical care. Participation in a similar clinical pilot program may be available to some families (e.g., those who live in rural areas may qualify for the Telephone Assisted Dementia Outreach Program, pending sustainment and availability which is unknown at the time this protocol is being submitted). However, no permanent services or "usual" treatment options similar to the one being studied are available at the Tuscaloosa VAMC.

19. Enlisting clinical expertise.

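### The count of completed action plans and homework has no denominator and can favor CC+C without better engagement; compare completion proportions instead

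*Combined protocol and SAP*

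**What the plan says.** Section 6 (Hypotheses for Aims 2 and 3) makes a directional prediction: "Treatment engagement (e.g. action plan completion, attendance) is also predicted to be higher in the CC+C group than in CC".

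Section 17 (Treatment Implementation, Fidelity, and Process Variables) lists two enactment measures. One is "the number of completed Action Plans and homework assignments in each group CC & CC+C". The other is "attendance/adherence to scheduled appointments". The same section records session length and indirect time under treatment receipt.

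Section 17 (Interventions Delivered) describes the arms:
- **CC.** A brief initial assessment identifies unmet needs, "which then immediately shapes development of concrete action plans". Homework is not mentioned.
- **CC+C.** For many families, action plans in the CC domains "will be implemented before the counseling protocol is initiated", and a further CC phase follows counseling. The counseling framework consists of "active engagement, assigning in-session and out-of-session exercises, reframing or restructuring cognitions, interpreting, and educating". Table 2 puts its content at about 6-8 sessions, with five required and four elective modules.

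Section 7 presents the counseling modules as layered onto CC when needed, for dyads too distressed to benefit fully from CC alone.

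**The concern.** A count of completed tasks reflects two things: how many tasks were set, and what share of them the dyad completed. Only the second is engagement. The first measure combines them, and it includes a type of task that the documents describe only for CC+C, the arm predicted to score higher.

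Nothing elsewhere in the plan separates the two. The ANCOVAs in Section 20 use change scores adjusted for a pre-treatment value, which engagement does not have, and no other analysis is given for it. Contact time is recorded but is not linked to the engagement comparison.

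At stake are the engagement hypothesis and part of the feasibility reading under Aim 2. Section 32 says the data will serve as pilot data for later grant proposals, so a difference in work assigned could be carried forward as a difference in engagement.

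**Working it through.** The documents state no engagement figure, so there is none to reproduce. All numbers of plans, homework items and completion rates below are assumptions.

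**Ratio of counts at equal engagement.** Let A be the action plans set per dyad in CC, H the homework items set in CC+C, r the number of action plans displaced by each homework item, and p the completion probability, the same in both arms.

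CC+C count / CC count = p(A − rH + H) / (pA) = 1 + (1 − r)H/A

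The completion probability cancels. With A from 6 to 14 and H from 6 to 8 (one item per counseling session):

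| Scenario | A = 14, H = 6 | A = 6, H = 8 |
|---|---|---|
| Fully additive (r = 0) | 20/14 = 1.43 | 14/6 = 2.33 |
| Half replacement (r = 0.5) | 17/14 = 1.21 | 10/6 = 1.67 |
| Full replacement (r = 1) | 1.00 | not possible, since H exceeds A |

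**How often the count would mislead.** A simulation used 3,000 runs per scenario and 25 dyads per arm (the 50 planned completers, assuming 1:1 allocation). Mean completion was 0.60 in both arms, with between-dyad variation in completion and in the number of plans set. Plans and homework were summed and compared with a two-sided 0.05 t-test. An unbiased measure would favor CC+C significantly in 2.5% of runs.

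Percentage of runs with CC+C significantly higher, homework fully additive:

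| Mean plans set | +3 homework | +5 homework | +8 homework |
|---|---|---|---|
| 5 | 75 | 98 | 100 |
| 10 | 34 | 68 | 96 |
| 15 | 19 | 43 | 80 |
| 20 | 13 | 29 | 57 |

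The CC+C mean was simply higher in 79% to 100% of these runs. Further scenarios, with 10 or 15 plans and 5 or 8 homework items:
- **Full replacement:** significantly higher in 3-4% of runs, mean higher in about 50%. The bias is gone.
- **Half replacement:** significantly higher in 18-60%.
- **Additive, with completion truly worse in CC+C (0.45 against 0.60):** the mean count still favored CC+C in 49-96% of runs. The expected counts show why. With 10 plans and 8 items, 18 × 0.45 = 8.1 against 10 × 0.60 = 6.0. With 15 plans and 5 items, 20 × 0.45 = 9.0 against 15 × 0.60 = 9.0.

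**Effect-size threshold.** Section 20 reads a between-group partial eta squared of .01 or more as potentially clinically meaningful. With 48 degrees of freedom this corresponds to t = √(0.01/0.99 × 48) = 0.70, which an unbiased measure exceeds in the direction of CC+C in 24.5% of trials. If the threshold were applied to the additive count, it would be met in favor of CC+C in 58% of runs (20 plans, +3) to 100% (5 plans, +5).

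**With a proportion.** Replacing the count by completed / assigned gave a significant result favoring CC+C in 2-3% of runs and met the .01 threshold in about 24%, both at their nominal levels.

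**The case against.** A reader might infer that engagement is measured only by this count and that the hypothesis is therefore close to guaranteed. The documents do not support that, for four reasons.

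- Attendance is a second measure in the same sentence and is named in the hypothesis. Read as a share of scheduled appointments, it is not inflated by extra sessions. This stands, although its scoring is not defined either.
- The hypothesis gives action plan completion as an example and does not name homework. Action plans exist in both arms, and nothing says CC+C sets more of them. Section 17 does not say that plans and homework are added together. This also stands, and it is a reason to compare the arms on the task they share.
- No total number of sessions is given for either arm. Counseling sits between two CC phases and may replace some CC contact. This stands, and with full replacement there is no bias. The layering language in Section 7 makes full replacement the less natural reading but does not exclude it.
- The measure's wording refers to both groups, so some homework may be recorded in CC. This stands, and homework should therefore be reported in whichever arm it is assigned.

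It can also be said that the text only monitors enactment and plans no test. That is so, but Section 6 makes a directional prediction and this is the only operational definition of action plan completion. The lack of a specified analysis does not correct the metric.

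**Conclusion.** The concern holds in a limited form. The first enactment measure can favor CC+C without better engagement, and nothing else in the plan corrects it. The size of the bias cannot be determined from the documents. It is zero if homework replaces action plans one for one, and it raises the CC+C count to about 1.4 to 2.3 times the CC count if homework is fully additive. That range rests on assumed figures of 6-14 plans and 6-8 homework items, equal completion in both arms, and summing of the two tasks.

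The stronger statement, that the hypothesis is bound to be supported, does not follow. Across the simulated scenarios with equal completion, the chance of a significant CC+C advantage ran from about 3% to about 100%, and attendance is a separate measure.

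The consequence is confined to the engagement hypothesis and the feasibility reading. The 6-month clinical outcomes do not depend on this measure.

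**What to change.** In Section 17, with a matching sentence in Section 20:

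- For the between-arm comparison, use action plans completed / action plans set, per dyad. Removing homework from the raw count would not be enough: if counseling displaces CC contact, a raw count of plans would be biased against CC+C.
- Score attendance explicitly as appointments kept / appointments scheduled, per dyad. CC+C seeks separate veteran calls where possible, so a raw attendance count could also differ by design.
- Report homework completed / assigned separately, in whichever arm it is assigned.
- Show raw counts beside the recorded contact time as delivered dose, not as evidence for the engagement hypothesis.

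The cost is a wording change and some extra logging: the interventionist must record the numbers set and scheduled alongside the numbers completed. Sample size, visits and participant burden do not change.

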The Dementia Services Mini-Screen³² will be used to identify dyads who are in distress and most likely to benefit from enhanced dementia services. This brief assessment tool was developed for use in primary care settings and has established cut-off points with strong sensitivity and specificity data that categorize individuals with dementia and their caregivers into low, moderate, or high stress groups based on the presence of behavioral disturbances and service needs (psychosocial and medical). Using this tool, dyads that endorse only low-moderate stress and few behavioral problems (0 or 1) will be excluded from the study. Excluded dyads will be offered a referral for clinical services. There will be no restrictions on gender or race for veterans with dementia or their caregivers.

Baseline, 6-month, and 12-month Assessments

Baseline and 6-month assessments will occur in the participant's homes or another convenient location of their choice (e.g., local public library). Informed consent will be the first thing addressed during the baseline assessment. Patient data will be collected interview-style by a trained assessor (research assistant) for the veteran with dementia, while the caregiver measures will be completed independently (paper and pencil). The brief 12-month assessment will occur over the telephone to reduce participant burden.

Measures

See assessment schedule described in Table 1 above. All measures are peer-reviewed and frequently used in the research literature with the proposed population. One measure that is likely less familiar to the IRB (i.e., Dyadic Adjustment Scale) has been uploaded with the submission package on IRBNet.

- a. **Subjective Health** will be measured using the sum of three items, with higher scores indicating better health.³⁴ **Subjective Stress** will be measured using two items, with higher ratings indicating increasing levels of stress.

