The study team has extensive clinical expertise in the delivery of interventions for individuals with dementia and their caregivers. See CVs and Bios uploaded and attached to this protocol for sample publications by the study team.

20. Description of the anticipated data and how the data will be analyzed to test the specific hypotheses results.

Study Design, Power, & Target Sample Size

We plan to recruit at least 70 dyads across the 3-5 year study period to ensure 50 completers at 6 months. This rate of 2 dyads per month is feasible given that there are 421 veterans with dementia currently receiving services from the TVAMC outpatient clinics (FY2013 clinical data). If 50% of them are in moderate to high distress (a conservative estimate based on our preliminary work), there would be over 200 individuals eligible. Power analyses were conducted to support this sample size (see attached grant text for more details).

Data Management and Analysis

Data Entry:

Data will be entered using Remark Office Optical Mark Recognition software and analyzed using Statistical Package for the Social Sciences (SPSS). Data analysis will be conducted using the VA Informatics and Computing Infrastructure (VINCI) server behind the VA firewall, as has been done for other TVAMC IRB approved studies. The research assistant will review all data for accuracy and will complete data tracking forms. A descriptive analysis of all assessment data will be conducted in order to examine distributional properties and correlations between the measures and the assumptions of statistical tests will be examined. Where necessary and sensible, data transformations, including the elimination of outliers, will be considered for variables with problematic properties.

Treatment of Missing Values:

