Missing values are unavoidable in applied clinical intervention research. Where possible, variables to index the number and reasons for missing values will be documented. Based on the distribution of these missing value indices we may choose to eliminate some participants from the analyses ("list-wise deletion"). The extent that missing values are related to the independent (treatment group) or outcome variables will be assessed and if necessary controlled for statistically. Individuals who complete at least four sessions of the intervention (CC or CC+C) will be included in final analyses when time 2 data are available. Strict intention-to-treat methodologies are too conservative for this relatively small initial pilot study.

Data Analysis:

A series of one-way between subjects analyses of covariance (ANCOVAs) will be used to examine the main effect of “group” on 6 month variables of interest while controlling for values at baseline. The dependent variable in these analyses will be change scores with pre-treatment scores as the covariate. This analysis is statistically equivalent to ANCOVA with pre-treatment scores as the covariate and 6-month scores as the dependent variable, but it has an interpretational advantage in that the change scores represent an individual treatment effect (change during treatment). The change scores also represent the interaction term of a 2 (Group) X 2 (Time) repeated measures ANOVA. Consequently, when other covariates are added to the ANCOVAs to address treatment moderation effects, those covariate effects will be directly interpretable as moderator effects. That is, the added terms will assess the effects of the covariates on changes during treatment irrespective of Group (essentially a Time by Covariate interaction). When the interaction (multiplicative product) of covariate and Group is also added as another term in the ANCOVA, that interaction term will supply the moderating effect of the covariate on change during treatment as function of Group (i.e., differential effect of treatment as a function of the covariate).

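### Section 20 lets participants be deleted list-wise, with no rule, once the missing-data pattern is known, and plans no group comparison of the eight scale rows collected at 12 months

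*Combined protocol and SAP*

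**What the plan says.** Section 20, Treatment of Missing Values, has three relevant parts.

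- Deletion is optional: "Based on the distribution of these missing value indices we may choose to eliminate some participants from the analyses". The text calls this list-wise deletion and states no cut-off.
- Adjustment is conditional: "The extent that missing values are related to the independent (treatment group) or outcome variables will be assessed and if necessary controlled for statistically". No method is named.
- The analysis set is restricted: "Individuals who complete at least four sessions of the intervention (CC or CC+C) will be included in final analyses", provided 6-month data exist. A strict intention-to-treat analysis is rejected as too conservative for a small pilot.

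Section 20, Data Analysis, plans separate ANCOVAs of group on "6 month variables of interest while controlling for values at baseline". Caregiver self-report, veteran self-report and proxy report form separate series. The only model at 12 months is a logistic regression of nursing home placement.

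Table 1 in section 17 marks eight scale rows at 12 months: Subjective Stress/Health, QOL-AD, Mutuality, Zarit, GAD-7, CES-D, FFMQ and DTI. The stated burden is under 50 minutes for the caregiver and under 30 for the veteran. Section 17 adds: "The brief 12-month assessment will occur over the telephone to reduce participant burden".

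**The concern.** A deletion rule chosen after the missing-data pattern is known can change who is analysed, and so the result, without any record of what was intended. Nothing says that the choice is made blind to group or to outcome.

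The option also pulls against other parts of the protocol. The note in section 12 says that available self-report or proxy data for severely impaired veterans will be kept for analysis, and section 10 lets caregivers take part alone. Such dyads have incomplete records by design and are the likeliest to be deleted. The Dyadic Adjustment Scale is meant for spousal dyads, so its blanks for other dyads are structural. If deletion ran across a set of scales that included it, non-spousal caregivers would go, although spousal status is a planned moderator.

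Separately, participants supply 12-month scores for which no group comparison is planned. Whether any effect on burden, mood or relationship quality persists would be left to analyses devised later.

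**Working it through.** **The plan's own figures.** Section 20 states: "We plan to recruit at least 70 dyads across the 3-5 year study period to ensure 50 completers at 6 months". The implied loss is (70 − 50)/70 = 28.6%. This is back-calculated: no dropout rate is given and completers are not defined. The sample size cannot be reproduced, because section 20 refers to grant text for the power analysis and gives no alpha, power, effect size or SD.

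**Count of scales.** Fourteen scale rows in Table 1 are measured at both baseline and 6 months. Eight are repeated at 12 months. Six are not: RMBPC, CSDD, EQ-5D, Social Engagement, Dyadic Adjustment and WHO-QOL-OLD. 8 + 6 = 14.

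**Cost of deleting completers.** If k of 50 participants with a 6-month score are removed, the standard error is multiplied by √(50/(50 − k)):

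- k = 2: √(50/48) = 1.021, a rise of 2.1%
- k = 5: √(50/45) = 1.054, a rise of 5.4%
- k = 10: √(50/40) = 1.118, a rise of 11.8%

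The plan does not say how large k might be.

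**Why discretion matters at this size.** Section 20 treats partial eta squared of .01 or more as potentially meaningful. With equal arms this is d = 2√(.01/.99) = 0.20. Assume 25 per arm (the allocation ratio is not stated). Removing one participant who lies 2 SD from the arm mean moves that mean by 2/24 = 0.083 SD, or 0.083/0.201 = 41% of the threshold.

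**What the 12-month scores add to the 6-month contrast.** Let m be the number who miss 6 months but return at 12, and r the correlation of 6- and 12-month scores given baseline. If all 50 with 6-month scores are also seen at 12 months, the ratio of standard errors (with versus without 12-month scores) is √(1 − r²m/(50 + m)). Both m and r are assumptions.

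- m = 0 (monotone dropout): 1.000, no gain at any r
- m = 5, r = 0.5: √(1 − 0.25 × 5/55) = 0.989
- m = 10, r = 0.6: √(1 − 0.36 × 10/60) = √0.94 = 0.970, effective n 50/0.94 = 53.2
- m = 20, r = 0.7: √(1 − 0.49 × 20/70) = √0.86 = 0.927

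The last case needs every one of the 20 non-completers to return. A simulation of 6,000 runs at r = 0.58 gave ratios of 1.000, 0.985, 0.978 and 0.947 for m = 0, 5, 10 and 20, in line with the formula.

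**The case against.** The case for leaving the plan alone has several parts.

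- Deletion is an option, not the stated method. The plan also records reasons for missingness and examines its relation to group and outcome. This stands, but neither step sets a rule for who is removed.
- A reader might multiply an assumed missing rate across the whole caregiver battery and infer that a large share of completers would be lost. The documents do not support that. The plan runs separate ANCOVAs, so deletion need not act on one complete-case set, and missingness on different scales is unlikely to be independent.
- A reader might infer a substantial loss of precision from leaving the 12-month scores out. For the 6-month contrast, which is the Aim 2 comparison, the gain is small and may be zero. Averaging the two visits would gain more but answers a different question. Section 17 expects placement for dyads lost to attrition to come from health records, which would supply no scale scores.
- It would also be too strong to say that nothing is learned about durability. Placement at 12 months is an Aim 3 outcome with its own model, and section 20 plans a descriptive look at all assessment data. What is missing is a group comparison of the 12-month scale scores.
- The fixed four-session rule is probably a larger source of bias than optional deletion. This is fair, and any remedy that analyses all randomised dyads must say that it overrides that rule.

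**Conclusion.** The concern holds in a limited form and should be acted on. The plan permits an exclusion with no rule, decided after the missing-data pattern is seen, and specifies no between-group analysis of eight scale rows that it collects at 12 months.

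The main gain from a change is the removal of that discretion and the use of data already collected. Precision is secondary. Avoiding deletion of 2, 5 or 10 of 50 completers avoids a 2%, 5% or 12% rise in standard error. The 12-month scores reduce the 6-month standard error by 0% to about 3%, where the upper figure assumes 10 returning non-completers and r = 0.6. More favourable assumptions give more, but the documents offer no missingness pattern or correlation to support them.

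**What to change.** 1. Delete the list-wise option.
2. For each of the eight repeated scale rows, fit a likelihood-based mixed model to all randomised dyads with any post-baseline score. Include group × time (6 and 12 months), baseline score × time, race and gender, with unstructured covariance. Keep the plan's separation of caregiver, veteran and proxy reports. The 6-month contrast is the main result and the 12-month contrast is second.
3. For the six scales measured only at baseline and 6 months, run the baseline-adjusted ANCOVA on everyone with that scale's 6-month score. Imputation without auxiliary variables would add essentially nothing here.
4. State that this replaces the four-session restriction as the main analysis set. The restricted set can be kept as a sensitivity analysis.
5. Partial eta squared may still be reported.

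The change needs no new data or visits. It costs more analysis work and a missing-at-random assumption, which should be stated. Caregivers move from in-person paper forms at 6 months to telephone at 12. The time term absorbs a shift common to both arms, but a shift that differs by arm would affect the 12-month contrast, so the change of mode should be reported with it.
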